- Grade 3 or 4 nausea, vomiting and diarrhea will be considered DLT only if not controlled by optimal therapy.
- Grade 3 biochemical abnormalities (e.g., lipase or bilirubin elevation) will only be considered DLT if accompanied by clinical consequences. Grade 3 or 4 electrolyte abnormalities will only be considered DLT if possibly related to study drug and not corrected by optimal replacement therapy.
- Results in discontinuation of therapy
- Any treatment-related death;

Hematologic DLT is defined as grade ≥ 3 neutropenia and/or thrombocytopenia with a hypocellular bone marrow ($<10\%$ cellularity) lasting for 42 days or more from Cycle 1 Day 1 in the absence of residual leukemia (i.e., with less than 5% blasts or residual leukemia by flow-cytometry or RT-PCR). Anemia will not be considered for the definition of DLT.

-Patients that are removed from study before day 28 for any reason other than toxicity and have not experienced DLT will be replaced. Patients who come off study earlier than 28 days during the DLT evaluation period may continue to receive protocol therapy if they are having clinical benefit, after discussion with the PI. The rationale for continuing therapy must be clearly documented in the patients chart.

-Patients who do not receive venetoclax on day 1 due to logistical and/or financial reasons, the DLT period will be extended to 28 days from the first dose of venetoclax. For evaluation of neutropenia-related DLT, the DLT period will be 42 days from the first dose of venetoclax.

5.2.1.5 Arm 1: We will first treat 6 patients at dose level 0 in the lead-in phase. If DLT occurs in $>/=2/6$ patients, this dose level would exceed the MTD, and 6 patients will be treated at the next lower dose level (i.e. dose level -1). The dose de-escalation (Table 5) will continue in cohorts of 6 until we reach a dose level at which $<2/6$ patients experience a DLT in the first 28 days. The dose level at which 0-1/6 patients experience a DLT in the first 28 days of treatment will be the MTD and will be used to treat an additional patients in the phase II portion of the study. If $>/=2/6$ patients experience DLT at dose level -4, the study will be revised to consider additional lower dose levels (based on potential synergistic toxicity).

If DLT is observed in the first 28 days of treatment in 0 or 1/6 at dose level 0, then dose level 0 will be used for the phase II portion of the study.

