Patients that are removed from study before day 28 for any reason other than toxicity and have not experienced DLT will be replaced.

5.2.1.6 Arm 2: We will first treat 6 patients at dose level 0 in the lead-in phase. If DLT occurs in $>/=2/6$ patients, this dose level would exceed the MTD, and 6 patients will be treated at the next lower dose level (i.e. dose level -1). If DLT occurs in $</=1/6$ patients, this dose level would not exceed the MTD, and 6 patients will be treated at the next higher dose level (i.e. dose level +1). The dose escalation or de-escalation (Table 5b) will continue in cohorts of 6 until we reach a dose level at which $<2/6$ patients experience a DLT in the first 28 days or if $</=1/6$ patients experience a DLT at dose level +1. The highest dose level at which 0-1/6 patients experience a DLT in the first 28 days of treatment will be the MTD and will be used to treat an additional 54 salvage 1 and 2 patients (Arm 2 Salvage Cohort) and 30 frontline AML $>/= 65$ years not candidates for induction therapy (Arm 2 Frontline cohort) in the phase II portion of the study. If $>/=2/6$ patients experience DLT at dose level -2, the study will be revised to consider additional lower dose levels (based on potential synergistic toxicity).

Patients that are removed from study before day 28 for any reason other than toxicity and have not experienced DLT will be replaced.

5.2.1.7 Arm 3: We will first treat 6 patients at dose level 0 in the lead-in phase (part a). If DLT occurs in $>/=2/6$ patients, this dose level would exceed the MTD, and 6 patients will be treated at the next lower dose level (i.e. dose level -1). The dose de-escalation (Table 5C) will continue in cohorts of 6 until we reach a dose level at which $<2/6$ patients experience a DLT in the first 28 days. The dose level at which 0-1/6 patients experience a DLT in the first 28 days of treatment will be the MTD. If $>/=2/6$ patients experience DLT at dose level -3, the study will be revised to consider additional lower dose levels (based on potential synergistic toxicity).

If DLT is observed in the first 28 days of treatment in 0 or 1/6 at dose level 0, then dose level 0 will be the MTD. The RP2D will be selected at the end of the lead-in phase and may be the MTD dose or a dose level lower than the MTD.

Patients that are removed from study before day 28 for any reason other than toxicity and have not experienced DLT will be replaced.

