If prolonged myelosuppression (more than 8 weeks) WITH evidence of a hypocellular marrow (marrow cellularity less than 5% without evidence of leukemia) is observed, 5-azacytidine and nivolumab OR 5-azacytidine with nivolumab and ipilimumab OR 5-azacytidine with nivolumab and venetoclax will be discontinued. Delays in start of subsequent cycles greater than 8 weeks will be acceptable only for patients who are deriving clinical benefit and after discussion with the principal investigator of potential risk/benefit ratio. If the peripheral counts do not recover (ANC <1 x10⁹/L and/or platelets <30 x10⁹/L) but there is evidence of residual leukemia in the bone marrow by morphology or flow-cytometry, subsequent cycles can be administered at the discretion of the treating physician not earlier than 21 days after the prior cycle.

5.2.2.5 For patients who discontinue therapy, the reason for treatment discontinuation will be captured.

5.2.2.6 Patients must receive at least 5 of 7 planned doses of azacitidine, 2 of 2 planned doses of nivolumab and 18 of 21 planned doses of venetoclax during the first 28 days on trial (i.e. during cycle 1) to be considered evaluable

Nivolumab and azacytidine during the DLT phase. Patients who receive less than these doses of each drug during the first 28 days on trial will not be considered evaluable during the DLT phase. However, if such patients develop a toxicity that would normally be considered a DLT this will still be captured as a DLT. Any toxicity that meets the criteria for DLT during the first 28 days of trial in a patient who has received at least one dose of either azacitidine, venetoclax or nivolumab will constitute a DLT. Patients not considered evaluable due to insufficient dosing and who do not develop a toxicity that is considered a DLT will be replaced. These patients may continue therapy on trial after discussion with the PI if they are having clinical benefit and the reasons for continuation and potential benefit/risk profile for the patient must be clearly documented in the medical records. In the expansion phase (part b), DLT will not be monitored. We will perform continuous safety monitoring every 5 patients for “drug-related non-hematological Grade 3/4 AE’s.”

5.2.2.7 Dose modifications other than the ones mentioned above can be considered after discussion with the PI and proper documentation of the rationale.

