11.3 Statistical Design

Part a. Lead-in phase

The MTD is defined as the highest dose level with < 2 out of 6 patients experience a DLT during the first 28 days of treatment. DLT is defined in section 5.2.2. The dosing schema for the combination treatment during the lead in phase is shown in Tables 5 and 5B in section 5.2.1.

Part b. Expansion phase

A. Arm 1 Relapsed/Refractory AML cohort (Aza+Nivo) (N=70: completed accrual and closed to accrual)

Historical data on similar patients show a ORR of 10-15%. The target ORR with the experimental treatment is 30%. This regimen of the combination treatment will be considered worthy of further investigation if it elicits an increase in ORR to 30% with acceptable toxicity. A >30% drug-related grade 3/4 toxicity rate is considered unacceptable. Thus, interim monitoring rules, assuming the prior distributions below, were constructed that meet the following two conditions,

- 1) Stop if $\text{Prob}\{ p(\text{ORR}, E) < p(\text{ORR}, H) + 0.15 \mid \text{data} \} > 0.99$, or
- 2) Stop if $\text{Prob}\{ p(\text{TOX}, E) > 0.30 \mid \text{data} \} > 0.95$,

Where $P(\text{ORR}, E)$ and $P(\text{TOX}, E)$ are the true ORR and toxicity rates for the combination treatment, and $p(\text{ORR}, H)$ is the true ORR rate of the standard treatment. The first rule provides for stopping the study if the data suggest that it is unlikely (i.e., probability < 1%) that ORR rate of the combination treatment is greater than the ORR rate of standard treatment by 15.0%. The second condition will stop the study early if excessive therapy-related grade 3/4 toxicity (>30%) is highly probable (i.e., probability >95.0%) for the combination treatment. Monitoring for toxicity and futility will not begin until 6 patients have been evaluated, and cohort size for future evaluations is 3.

The monitoring rule for the toxicity rate, based on these assumptions and monitoring conditions above is found in Table 9. **For example, accrual will cease if 5 or more patients experience toxicities among the first 6 patients.**

| |
|--|
| Table 9. Stop accrual if the number of drug-related grade 3/4 toxicities is greater than or equal to indicated (i.e., # patients with toxicities) among the number of patients evaluated |
|--|

Nivolumab and azacytidine

| # patients evaluated | 3 | 6 | 9 | 12 | 15 | 18 | 21 |
|----------------------------|-------|-------------------------------------|-------|-------|-------|-------|-------|

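### Arm 3 lead-in: for patients who start venetoclax late, the extended DLT period in 5.2.1.4 is not carried into the evaluability rule (5.2.2.6), the 28-day DLT period (5.2.2.1) or the MTD rules (5.2.1.7, 11.3)

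*Combined protocol and SAP*

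**What the plan says.** The Arm 3 instructions under 5.2.1.7 allow azacitidine and nivolumab to begin while venetoclax is still being obtained, and state that a late venetoclax start is not a deviation. The plan therefore expects late starters.

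The sections that decide who and what is counted are these:

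- **DLT definition (5.2.1.4, below Table 5C).** If venetoclax is not given on day 1 for logistical or financial reasons, "the DLT period will be extended to 28 days from the first dose of venetoclax". For neutropenia, "the DLT period will be 42 days from the first dose of venetoclax".
- **Evaluability (5.2.2.6).** A patient needs at least "18 of 21 planned doses of venetoclax during the first 28 days on trial", besides minimum azacitidine and nivolumab doses. "Patients not considered evaluable due to insufficient dosing and who do not develop a toxicity that is considered a DLT will be replaced".
- **DLT capture (5.2.2.6).** The general rule is worded as "Any toxicity that meets the criteria for DLT during the first 28 days of trial", for any patient who has had at least one dose of any of the three drugs.
- **MTD rule for Arm 3 (5.2.1.7).** "The dose level at which 0-1/6 patients experience a DLT in the first 28 days of treatment will be the MTD".
- **MTD rule in the statistics section (11.3).** The highest level with "< 2 out of 6 patients experience a DLT during the first 28 days of treatment".
- **Lead-in DLT period (5.2.2.1).** 28 days; cycle 2 is not to start earlier than that.

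Section 5.3 counts Day 1 of each cycle from azacitidine, so the 28-day wording is most naturally read as running from azacitidine, not venetoclax.

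**The concern.** The late-start extension appears in one place only. The evaluability rule, the 28-day DLT period and both statements of the MTD rule do not mention it. Two things then depend on which section the team follows at the dose-level review: whether a late starter is one of the six, and whether a DLT after trial day 28 is counted.

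The decision turns on 0-1 versus 2 events in six patients, so a single event or a single replacement can change it. The lead-in result informs the dose for two expansion cohorts of 30 patients each. In those cohorts 5.2.2.6 says DLTs are no longer monitored, although drug-related non-haematological grade 3/4 events are reviewed every five patients.

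**Working it through.** **Plan's own figure.** Section 11.2 gives 18 patients for the Arm 3 lead-in: 3 dose levels × 6 = 18, which reproduces. The plan states no operating characteristics for the lead-in rule, so there is no further figure to match.

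**Inputs.** Planned venetoclax in cycle 1 is Days 1-21 (5.2.1.7). The evaluability minimum is 18 doses within 28 days (5.2.2.6). The extended period is 28 days from the first venetoclax dose, or 42 for neutropenia (5.2.1.4). Under 5.2.1.7, venetoclax is held after the day 21 marrow if that shows remission or aplasia/hypoplasia; otherwise it continues to day 28.

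**Dose count.** For a first venetoclax dose on trial day s and a last dose on day L, the most doses possible is L − s + 1.

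| Start day s | Doses if L = 21 | Doses if L = 28 | 28-day period ends (s + 27) | Days after day 28 (s − 1) | Neutropenia period ends (s + 41) |
|---|---|---|---|---|---|
| 4 | 18 | 25 | 31 | 3 | 45 |
| 5 | 17 | 24 | 32 | 4 | 46 |
| 8 | 14 | 21 | 35 | 7 | 49 |
| 11 | 11 | 18 | 38 | 10 | 52 |
| 12 | 10 | 17 | 39 | 11 | 53 |

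With dosing through day 28, 29 − s ≥ 18 requires s ≤ 11. With dosing that ends on day 21, 22 − s ≥ 18 requires s ≤ 4. Day 12 is therefore the most lenient cut-off and day 5 applies when venetoclax stops on day 21. For starts on days 5-11, evaluability can depend on marrow response: a patient held on day 21 fails the count, while one continued to day 28 can meet it.

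**Events.** With a day 11 start, the 5.2.1.4 period is trial days 11-38. A DLT on days 29-38 is inside that period and outside the 28-day windows of 5.2.2.6, 5.2.1.7 and 11.3, unless 5.2.1.4 is read as overriding them.

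**Effect on the decision rule.** A level is accepted if 0 or 1 of 6 patients has a DLT. Assume a 25% DLT risk, of which 5 points fall after trial day 28 in a late starter and are not counted.

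- No late starter: 0.75⁶ + 6 × 0.25 × 0.75⁵ = 0.178 + 0.356 = 0.534.
- One late starter (one patient at 20%, five at 25%): P(0) = 0.75⁵ × 0.8 = 0.190; P(1) = 5 × 0.25 × 0.75⁴ × 0.8 + 0.75⁵ × 0.2 = 0.316 + 0.047 = 0.364; total 0.554.
- All six late: 0.8⁶ + 6 × 0.2 × 0.8⁵ = 0.262 + 0.393 = 0.655.

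A second illustration assumes a constant DLT hazard over the 28 days from first venetoclax and a day 11 start, so that 18 of 28 days are counted. A true 30% rate then becomes 1 − 0.7^(18/28) = 0.205 for a late starter. The chance of accepting the level goes from 0.420 to 0.454 with one late starter, and to 0.643 if all six are late.

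**The case against.** The strongest reply is that 5.2.1.4 is an express exception for one subgroup, and the other sections state the default that it extends. A specific rule normally overrides a general one. Section 5.2.2.6 supports this in part: it says what will count as a DLT without saying that nothing later can. It also says, with no time limit, that a toxicity in an under-dosed patient which would normally be a DLT is still captured. A reader might infer that the plan discards toxicity after trial day 28. The documents do not go that far, and this part of the objection stands. It does not help the venetoclax dose count, for which no section gives an exception.

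A second reply is that azacitidine is normally finished by day 7, or day 9 on the named weekend-break schedules. A patient who starts venetoclax on day 12 or later has then usually had no concurrent azacitidine in cycle 1, and replacing that patient can be defended. That is fair, but the plan does not say that this is the intent, and it offers the same patient an extended DLT period that has no effect unless a DLT occurs.

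Third, 5.2.2.1 sets a floor for cycle 2 and ties it to the DLT period, so it is not clear permission to begin cycle 2 inside an extended period. That also stands; what is missing is a statement for late starters.

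Finally, the plan says only that some patients may be delayed, so the numerical effect may be small.

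**Conclusion.** The inconsistency is real and bears on the MTD decision. As written, a DLT-free patient who starts venetoclax on day 12 or later must be replaced despite full observation under 5.2.1.4. The same holds from day 5 if venetoclax stops on day 21. For DLTs after trial day 28 the plan is ambiguous: they count under 5.2.1.4 and fall outside the other stated windows unless 5.2.1.4 prevails. Section 11.3 is affected through the DLT window only, since it sets no dose count.

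The size cannot be fixed from the documents, because neither the number of late starters nor the timing of DLTs is given. Under the 25%/5-point assumption, one late starter adds about 2 percentage points to the chance of accepting the level (0.534 to 0.554). A reader might infer a rise of about 12 points (to 0.655), but that requires all six patients to start late and every late event to go uncounted. Where late events are left out, the shift is toward accepting the level.

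**What to change.** Reconcile 5.2.2.6, 5.2.1.7, 5.2.2.1 and 11.3 with the extended DLT period in 5.2.1.4, so that one stated window decides which late-start patients are evaluable and which DLTs enter the fewer-than-2-of-6 rule.

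In 5.2.2.6, limit the change to the venetoclax dose count and the DLT capture window, and leave the azacitidine and nivolumab counts on their own clock. Section 5.2.1.4 covers the DLT period only. Moving every dose minimum to the first venetoclax dose would also break the azacitidine count: on a Days 1-7 schedule, a day 4 venetoclax start leaves at most 4 azacitidine doses (days 4-7) in that cycle against the required 5 of 7.

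State that the dose-level review waits until the last patient's applicable window has closed, and reconcile the earliest cycle 2 start in the lead-in with that window.

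The cost is protocol wording, and a lead-in review that may be delayed by as long as the venetoclax start was delayed.

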Table 5C: Arm 3: Dose levels of 5-azacytidine, nivolumab and venetoclax during the lead-in phase (part a)

| Dose level | 5-azacytidine (mg/m ² /d, Days 1-7) | Nivolumab (mg/kg, day 8 and 22) | Venetoclax (400mg or equivalent) |
|---|---|------------------------------------|-------------------------------------|
| -2 | 75 | 1.0 | D1-14 |
| -1 | 75 | 1.0 | D1-21 |
| 0 (starting dose and target dose)) | 75 | 3.0 (starting dose) | D1-21 |

The goal of the lead-in phase is to identify the MTD i.e. the dose at which <2/6 patients experience DLT. During the lead-in phase the dose/s/duration of nivolumab and/or venetoclax may be reduced if 2 or more patients experience DLT at any given dose as shown in Table 5C. The RP2D will be selected at the end of the lead-in phase and may be the MTD dose or a dose level lower than the MTD.

Once the RP2D is decided the expansion (part b) will open in 2 cohorts: Frontline cohort (n=30) and Salvage Cohort (n=30) with eligibility as defined in 4.2.1. See “statistics” section for more details.

After the lead-in (part a) the dose of nivolumab may NOT be reduced in the expansion (part b) of the study. For potential nivolumab related AEs only dose interruptions will be permitted. Dose reductions or escalations of venetoclax and 5-azacytidine are permitted in the expansion (part b) of the study and dose reductions or escalations of 5-azacytidine or venetoclax beyond those mentioned in table 5C or 5.3.2 should be discussed with the PI and documentation of the justification recorded in the chart. Only Salvage patients as defined in Inclusion criteria 4.1B will be enrolled during in the lead-in phase.

The dose and /or schedule of administration is subject to modification pending information from ongoing clinical trials of nivolumab or ipilimumab or venetoclax as a single agent and in combination with other drugs.

DLT is defined as clinically significant non-hematologic adverse event or abnormal laboratory value assessed as unrelated to disease progression, intercurrent illness, or concomitant medications and occurring during the first cycle on study that meets any of the following criteria:

- CTCAE Grade 3 AST (SGOT) or ALT (SGPT) for ≥= 7 days or grade 3 hyperbilirubinemia for ≥= 7 days
- CTCAE Grade 4 AST (SGOT) or ALT (SGPT) of any duration
- All other clinically significant non-hematological adverse event that is Grade 3 or 4 according to the NCI common terminology criteria version 4.0 with the following exceptions:

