- Venetoclax will be administered orally daily on Days 1-21 of the first cycle; and Days 1-14 for subsequent cycles.
- In cycle 1, patients should undergo a bone marrow aspiration and biopsy on day 21 (+/- 4 days). Patients who achieve marrow remission (i.e. bone

Nivolumab and azacytidine marrow blasts <5% by morphology) or marrow aplasia/hypoplasia (</=10% cellularity or insufficient sample) should discontinue venetoclax for the remainder of the cycle and be monitored for count recovery.

- a) If the Day 21 bone marrow shows <5% blasts, the venetoclax should be held, and cycle 2 should not be initiated till ANC>0.5 and platelets are >30K without platelet transfusion support for >5 days.
- b) If the Day 21 bone marrow shows aplasia/hypoplasia (</=10% cellularity or insufficient sample), the venetoclax should be held on Day 21, and a repeat bone marrow should be performed on Day 28 (+/- 4 days) for response and MRD assessment. If the Day 28 bone marrow shows >/=5% blasts proceed with cycle 2 if this is in the best interest of the patient (those with C1D28 bone marrow >/=5% are allowed to receive 21 days of venetoclax in cycle#2). If the Day 28 bone marrow shows <5% blasts, the venetoclax should continue to be held, and cycle 2 should not be initiated till ANC>0.5 and platelets are >30K without platelet transfusion support for >5 days. If the Day 28 bone marrow shows persistent aplasia/hypoplasia (</=10% cellularity or insufficient sample) continue to hold the venetoclax and repeat a bone marrow in approximately 10-14 days.
- c) If a bone marrow remission (<5% blasts) or aplasia/hypoplasia is not confirmed on the Day 21 bone marrow, patients should continue venetoclax until day 28 and have a repeat bone marrow on Day 28 (+/- 5 days). If the Day 28 bone marrow shows >/=5% blasts proceed with cycle 2 if this is in the best interest of the patient (those with C1D28 bone marrow >/=5% are allowed to receive 21 days of venetoclax in cycle #2). If the Day 28 bone marrow shows <5% blasts or aplasia/hypoplasia follow steps outlined in "a" and "b" above.
- d) Treatment interruptions and dosing schedules other than the ones mentioned above can be considered after discussion with the PI and proper documentation of the rationale.
- e) Of note the nivolumab infusion will continue as scheduled and will not be impacted or adjusted based on venetoclax dosing schema or venetoclax related delays.

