11.2 Sample Size

Arm 1:***Part a. Lead-in phase***

The primary objective of the lead-in phase is to determine the safety of nivolumab in combination with 5-azacytidine in patients with refractory/ relapsed AML. Up to 30 patients will be accrued into the lead-in part of the study.

Part b. Expansion phase

- A. Up to 70 patients (including 6 patients treated at the MTD from the lead-in part) with relapsed/refractory AML will be recruited for the Arm 1 Salvage cohort .
- B. Up to 40 newly diagnosed older AML patients (age ≥ 65) will be recruited for the Arm 1 Frontline older cohort .

Arm 2:**Part a. Lead-in phase**

The primary objective of the lead-in phase is to determine the safety of nivolumab with ipilimumab in combination with 5-azacytidine in patients with refractory/ relapsed AML. Up to 24 patients will be accrued into the lead-in part of the study.

Part b. Expansion phase

- A. Up to 54 patients (including 6 patients treated at the MTD from the lead-in part) with relapsed/refractory AML will be recruited for the Arm 2 Salvage cohort.
- B. Up to 30 newly diagnosed older AML patients (age ≥ 65) will be recruited for the Arm 2 Frontline older cohort.

The efficacy of the combination will be measured by the overall response rate (ORR), defined as CR (complete remission) + CR_p (complete remission with incomplete platelet recovery) + CR_i (complete remission with incomplete count recovery) + PR (partial response) + marrow clearance of blasts + hematologic improvement (HI) in platelets, hemoglobin, or ANC within 3 months of treatment initiation among adult patients with refractory/ relapsed AML AND newly diagnosed older patients with AML. ORR and toxicity will be monitored simultaneously using the Bayesian approach of Thall, Simon, Estey (1995, 1996) and the extension by Thall and Sung (1998).

Arm 3:**Part a. Lead-in phase**

The primary objective of the lead-in phase is to determine the safety of nivolumab with 5-azacytidine and venetoclax in patients with refractory/ relapsed AML. A total of 18 patients (3 dose levels with a maximum of 6 patients at each dose level) will be accrued into the lead-in part of the study.

Part b. Expansion phase

- A. A total of 30 patients (excluding 6 patients treated at the MTD from the lead-in part) with relapsed/refractory AML will be recruited for the Arm 3Salvage cohort.
- B. A total of 30 newly diagnosed older AML patients (age ≥ 65) will be recruited for the Arm 3 Frontline older cohort.

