| | 0.90 | 0.1194 |
| 0.40 | 0.60 | 0.8740 |
| | 0.70 | 0.6569 |
| | 0.80 | 0.4589 |
| | 0.85 | 0.4109 |
| | 0.90 | 0.3907 |
| 0.50 | 0.60 | 0.9465 |
| | 0.70 | 0.8543 |
| | 0.80 | 0.7702 |

| Nivolumab and azacytidine | | |
|---------------------------|---------------|------------------|
| True Toxicity Rate | True ORR Rate | PROB(Stop Early) |
| | 0.85 | 0.7498 |
| | 0.90 | 0.7412 |

The Investigator is responsible for completing an efficacy/safety summary report, and submitting it to the IND Office Medical Affairs and Safety Group, for review and approval. This should be submitted as follows:

Lead-in Phase:

Every 6 evaluable patients complete cycle 1 of study therapy before advancing/changing dose levels.

Expansion Phase:

After the first 5 evaluable patients per cohort, complete 3 months of study treatment, and every 5 evaluable patients per cohort, thereafter.

A copy of the cohort summary should be placed in the Investigator's Regulatory Binder under "sponsor correspondence".

Statistical Analysis Plan

All patients who received any dose of the study agent will be included in the analysis for efficacy and safety. Demographic/clinical characteristics (including duration of response) and safety data of the patients will be summarized using descriptive statistics such as mean, standard deviation, median and range. For the primary efficacy analysis, we will estimate the ORR for the combination treatment, along with the 95% confidence interval. Patients who drop out of the study before completing all the cycles will be treated as "failures" for the primary analysis. Overall response rate (ORR) during the study period will also be presented with the 95% confidence interval. The association between ORR and patient's clinical characteristics will be examined by Wilcoxon's rank sum test or Fisher's exact test, as appropriate. Toxicity type, severity and attribution will be summarized for each patient using frequency tables.

The distribution of time-to-event endpoints (DFS and OS) including overall survival and progression free survival will be estimated using the method of Kaplan and Meier.

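### Arm 3 lead-in level -2 plans 14 venetoclax doses but DLT evaluability requires 18, so patients who follow that schedule count only if they have a DLT

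*Combined protocol and SAP*

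**What the plan says.** Table 5C (section 5.2.1.4) defines three Arm 3 lead-in levels. Levels -1 and -2 share azacitidine 75 mg/m² and nivolumab 1.0 mg/kg. They differ only in venetoclax, days 1-21 at level -1 and days 1-14 at level -2. The text under the table makes duration a de-escalation step: the "dose/s/duration of nivolumab and/or venetoclax may be reduced if 2 or more patients experience DLT at any given dose".

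Section 5.2.2.6 defines who is evaluable for DLT. For venetoclax the patient must have received "18 of 21 planned doses of venetoclax during the first 28 days on trial (i.e. during cycle 1) to be considered evaluable". No other figure is given for level -2. On patients below the minimum it says two things:

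- "if such patients develop a toxicity that would normally be considered a DLT this will still be captured as a DLT"
- "Patients not considered evaluable due to insufficient dosing and who do not develop a toxicity that is considered a DLT will be replaced"

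Section 5.2.1.7 makes the MTD the level with 0-1 DLT in 6 patients over 28 days. Section 11.2 plans "3 dose levels with a maximum of 6 patients at each dose level".

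The cycle-1 dosing text in section 5.2.1.7 carries no qualification by level: "Venetoclax will be administered orally daily on Days 1-21 of the first cycle; and Days 1-14 for subsequent cycles". Section 3.1 also gives days 1-21 for the first cycle. Rule (c) in section 5.2.1.7 continues venetoclax to day 28 when the day-21 marrow shows neither remission nor aplasia/hypoplasia.

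**The concern.** At level -2 the planned exposure is below the evaluability minimum. Counting every DLT while replacing under-dosed DLT-free patients is a reasonable convention when under-dosing is the exception. Here under-dosing is the schedule itself, so entry to the denominator depends on the outcome. A DLT-free patient can count only by being extended under rule (c), which means having persistent blasts and taking more venetoclax than the level specifies. This pushes a tolerable level towards failure, and any pass would rest on DLT-free patients who were not treated on days 1-14. Level -2 is the lowest level in Table 5C, so a wrong failure would discard a usable schedule after exposing further relapsed or refractory patients to it.

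**Working it through.** **The plan's own figure.** 3 levels × 6 patients = 18, as in section 11.2.

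**Doses against the minimum.** Days 1-14 give 14 doses; 18 are required; the shortfall is 4. Levels 0 and -1 plan 21 doses and are unaffected.

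**Rule (c) at level -2.** Suppose venetoclax stops after day 14 and resumes the day after a marrow on day m, through day 28. The total is 14 + (28 - m). For m = 21 this is 21. Across the ±4-day window (m = 17 to 25) it runs from 25 down to 17, so a day-25 marrow still falls short.

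**Chance that level -2 passes.** The true DLT rate p and the share q of DLT-free patients extended to 18 or more doses are assumptions; the documents give neither. The DLT fraction among counted patients is r = p / (p + (1 - p)q), and P(pass) = P(X ≤ 1) with X ~ Bin(6, r).

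| p | q | r | P(pass) |
|---|---|---|---|
| 0.10 | 0 | 1 | 0 |
| 0.10 | 0.25 | 0.308 | 0.404 |
| 0.10 | 0.50 | 0.182 | 0.700 |
| 0.10 | 1 (all evaluable) | 0.10 | 0.886 |
| 0.20 | 0 | 1 | 0 |
| 0.20 | 0.25 | 0.500 | 0.109 |
| 0.20 | 0.50 | 0.333 | 0.351 |
| 0.20 | 1 (all evaluable) | 0.20 | 0.655 |

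The zero at q = 0 holds at every DLT rate.

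**Patients treated at q = 0.** If replacement continues as written, the cohort closes only at a second DLT, after 2/p patients on average: 20 at p = 0.10 and 10 at p = 0.20. If the section 11.2 cap of 6 is enforced instead, the chance of two or more DLTs at p = 0.10 is 1 - 0.886 = 0.114. Otherwise the level ends without six evaluable patients and so without a decision.

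**Chance that level -2 opens.** This is the product of P(X ≥ 2 of 6) at level 0 and at level -1.

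| DLT rate, level 0 | DLT rate, level -1 | P(level -2 opens) |
|---|---|---|
| 0.10 | 0.10 | 0.114 × 0.114 = 0.013 |
| 0.20 | 0.20 | 0.345 × 0.345 = 0.119 |
| 0.30 | 0.30 | 0.580 × 0.580 = 0.336 |
| 0.40 | 0.40 | 0.767 × 0.767 = 0.588 |
| 0.20 | 0.10 | 0.345 × 0.114 = 0.039 |
| 0.30 | 0.20 | 0.580 × 0.345 = 0.200 |
| 0.40 | 0.30 | 0.767 × 0.580 = 0.445 |

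**Unconditional loss at q = 0.** With the same rate at all three levels, multiply P(opens) by P(pass) with all evaluable: 0.013 × 0.886 = 0.01 at 0.10; 0.119 × 0.655 = 0.08 at 0.20; 0.336 × 0.420 = 0.14 at 0.30; 0.588 × 0.233 = 0.14 at 0.40. The loss is larger if level -2 is much the safer. With 0.30 at both higher levels and 0.10 at level -2, it is 0.336 × 0.886 = 0.30.

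**The case against.** The strongest reply is that level -2 also receives venetoclax on days 1-21 in cycle 1. Sections 3.1 and 5.2.1.7 say so without exception, section 5.2.2.6 itself speaks of 21 planned doses, and the Table 5C column does not name a cycle. Section 5.2.1 gives days 1-21 for the first cycle and can be read as letting the dose level govern later cycles only. On that reading 18 doses are attainable and the selection disappears. It does not rescue the level, however: level -2 would then be the same treatment as level -1 throughout the 28-day window, and the 14-day schedule would never be tested. Table 5C is titled for the lead-in, and the text beneath it makes duration reducible after DLTs, so the table is the better reading. The conflict needs correcting either way.

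Second, staff might read the minimum as a proportion and apply 12 of 14. That is sensible, but section 5.2.2.6 states dose counts and makes anyone below them non-evaluable.

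Third, sponsor review (sections 5.2 and 11.3) could catch the problem before level -2 opens. It could, but it does not change the minimum, and the section 11.3 lead-in trigger is itself stated in evaluable patients: "Every 6 evaluable patients complete cycle 1 of study therapy before advancing/changing dose levels".

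What stands is that this is a contingency. Related lead-ins without venetoclax had few DLTs: none in 6 for azacitidine plus nivolumab in section 2.3 C (1 in 6 in section 5.2.2.8), and none in 12 with ipilimumab (section 2.3 D). The 20 or 10 patients follow from the replacement rule read literally and would exceed the cap of 6 per level. The expansion cohorts' monitoring rules are unaffected.

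**Conclusion.** The concern holds. As written, no DLT-free patient treated on days 1-14 can be counted at level -2, so the MTD rule cannot be met on that schedule. With rule (c) extensions, the chance of a pass falls from 0.89 to between 0.40 and 0.70 at a DLT rate of 0.10, and from 0.66 to between 0.11 and 0.35 at 0.20, for extension shares of 0.25 to 0.50. Those figures rest on assumed DLT rates and shares; the 14-against-18 shortfall and the zero without extensions do not. The consequence is conditional on two failed levels above, so this should be corrected before level -2 could open but does not affect levels 0 and -1.

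**What to change.** - State that Table 5C sets the cycle-1 venetoclax days in the Arm 3 lead-in, and align sections 3.1, 5.2.1 (Arm 3) and 5.2.1.7 with it, including the delayed-start text that carries dosing through the day-21 marrow.
- In section 5.2.2.6, scale the venetoclax minimum to the level's planned doses. The present proportion, 18/21 = 86%, gives 12 of 14 at level -2. That figure is a suggestion; the documents do not give one.
- State whether rule (c) applies at level -2 during the DLT period. This is a clinical choice: excluding it keeps the level as specified, while allowing it gives longer cycle-1 venetoclax to patients with persistent blasts.

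The cost is an amendment to wording, with no added visits, tests or patients. If rule (c) is excluded at level -2, patients there with persistent blasts lose the longer venetoclax course in cycle 1.
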